#### **11.8 Participant compensation**

Participants will participate in the trial in the course of their usual clinic visits, so should incur no extra costs related to transport and a minimal time burden. DBS collection at baseline may cause minimal discomfort.

In Lesotho, no compensation will be paid to participants. In Malawi, \$10 equivalent in Malawi kwacha will be paid to participants.

## **12 QUALITY CONTROL AND QUALITY ASSURANCE: DESCRIPTION OF MEASURES**

### **12.1 Risk management and possible constraints**

#### **12.1.1 Risks to viability of the study**

We do not anticipate any serious threats to the study. Potential issues that we will navigate is the COVID-19 pandemic, which may reduce the number of people presenting to clinics and/or lead to change in dispensing and documentation practices. Another issue is lower than anticipated recruitment. If sample size is not reached after the anticipated 12 months recruitment period, we foresee a prolongation of recruitment at sites to be defined.

#### **12.1.2 Risks and benefits for participants**

Risks for participants are relatively small. Based on existing evidence, there is equipoise between the two interventions, as outlined in section 2 (background), section 0 (safety) and section 11 (ethics).

Apart from the group-specific timing of ART initiation, participation in the SaDAPT trial will not influence the care that participants receive at the study sites by routine clinical staff. Participants will be encouraged to return to the study clinic any time during the follow-up period to have medical complaints investigated and to receive care, as per local standards. The tracing of participants to ascertain the study endpoint between week 31 and 40 will be used to re-link participants to care and will thus help to minimize the number of participants lost to potentially life-saving HIV care.

The evidence that we aim to generate with this trial may help to establish the optimal approach to ART initiation in this large subgroup of PLHIV and has thus the potential to significantly improve health outcomes of these patients in the future.

### **12.2 Monitoring and Auditing**

The Swiss TPH's Clinical Operations Unit (COU) will be responsible for developing the monitoring strategy. A monitoring plan will be developed before the study start. The monitoring will entail a systematic examination of study related activities and documents. Onsite monitoring in Lesotho will be conducted by a local monitoring team under the supervision of the COU. Onsite monitoring in Malawi will be conducted by the Malawi Liverpool Wellcome Clinical Research Support Unit (CRSU) in accordance with the monitoring plan provided by COU.

At least one monitoring visit at selected sites in both study countries will assess whether the study activities were conducted, and data were recorded, analyzed and accurately reported according to the approved protocol, GCP, and the applicable regulatory requirements.

The study documentation and the source data will be accessible to the monitoring team, the IECs and regulatory authorities upon request. The investigators will assist the inspectors in their duties, if requested.

All involved parties must keep the participant data strictly confidential.

### **12.3 Translations - Reference language**

The reference language of the study documents is English, official language in both study countries. Whereas in both countries, healthcare professionals and thus all study staff is fluent in written and spoken English, this may not be the case for all participants. Therefore, the informed consent forms (ICFs) will be translated from an English master document into the local languages Sesotho (for Lesotho) and Chichewa (for Malawi) while all other study documents will be available in English exclusively. The quality of translation of the ICFs will be ensured by back-translation as well as by quality and comprehension checks by bilingual individuals not involved in the translation.

## 12.4 Storage of biological material and related health data

We will collect plasma and DBS samples for storage and subsequent analysis including HIV genotyping, resistance testing or other related research purposes. The samples collected in Lesotho will be stored for a maximum of five years at the laboratory of Seboche Hospital. All samples collected in Lesotho fall under the biobank agreement ("Biobanking regulations, v2.0") approved by the ethics committees in Lesotho and Switzerland.

In Malawi samples will be held for up to five years at the TB laboratory Kamuzu University of Health Sciences for studies related to same day ART or TB screening. Samples will remain the property of the government of Malawi. Participants will be asked to consent to samples being transferred out of Malawi for tests not available in Malawi. For instance, we plan to test for HIV genetic resistance – we are hopeful that by the end of the study this will be available in Malawi. However, should this not be the case we will apply for a Material Transfer Agreement (MTA) for shipping.

## 12.5 Project timeline

Quarter of year	2022				2023				2024			
	1	2	3	4	1	2	3	4	1	2	3	4
Preparation of study protocol, agreement, ethics approval, briefing of stakeholders, logistics preparation, recruitment of staff	x	x	x									
Recruitment of participants				x	x	x	x	x				
Follow-up period including tracing				x	x	x	x	x	x	x	x	x
Primary endpoint assessment					x	x	x	x	x	x	x	x
Data analysis, writing of publication									x	x	x	

## **13 FUNDING**

This trial is funded by a grant from the Swiss National Science Foundation (Project Number 32003B\_205053/1), obtained by the Sponsor-Investigator [name]. We attest that there is no conflict of interest and that this study will be conducted independently of outside influences in terms of specific intellectual, financial, and proprietary agendas. The funding source will have no role in the design of the trial, and will not be involved in data collection, data analysis, interpretation of the results, and writing of the manuscript.

## **14 DISSEMINATION OF RESULTS AND PUBLICATION POLICY**

### **14.1 Dissemination to scientific community; including lead in publications**

International scientific conferences and publications in scientific peer-reviewed journals will serve for wider dissemination of results. The requirements of the CONSORT statement will be fulfilled. The study has been registered on ClinicalTrials.gov (NCT05452616) prior to the start of the trial and a summary of the study protocol will be published in a peer-reviewed journal. The current version of the International Committee of Medical Journal Editors (ICMJE) recommendations is applicable regarding authorship eligibility. The use of professional writers is not intended.

An anonymized dataset of the study will be deposited at a public data repository once main-findings have been published.

### **14.2 Information of community and policy makers**

Results of this study will be shared with stakeholders at district and national level in both study countries. In Lesotho, health care workers and stakeholders will be informed about the findings during district meetings headed by the District Health Management Team (DHMT) and at national level, the national research symposium of the Ministry of Health will serve as a platform to share the results and discuss their implications among the policy makers. In Malawi, results will be shared with the Blantyre District Health Office, the Department of HIV/AIDS and relevant HIV providing partners.

We will also organise results dissemination events in participating health facilities for staff and patients to hear the results of the study they participated in.

## 15 ART INITIATION COHORT SUB-STUDY

In parallel to the SaDAPT trial, we will observationally follow-up all PLHIV (re)initiating ART at the study sites in a prospective ART initiation cohort, independent of whether they are eligible for participation in the SaDAPT trial.

### 15.1 Rationale

The SaDAPT trial enrolls PLHIV (re)initiating ART who present with symptoms of a presumptive TB infection according to W4SS. However, the sensitivity and specificity of the W4SS for TB case finding in PLHIV is limited and a considerable proportion of PLHIV are known to have subclinical TB disease before initiating ART. It is unclear how relevant presence or absence of TB symptoms are for clinical management and outcomes, including occurrence of active TB. Enrolling all PLHIV (re)initiating ART at the study facilities into an observational cohort in parallel to the recruitment for the SaDAPT trial shall allow to understand if and if yes to what extent characteristics and outcomes among PLHIV with and without TB symptoms who are (re)initiating ART differ and thus also help to weigh external validity and generalizability of the SaDAPT trial results.

### 15.2 Objectives

The objectives of the ART initiation cohort are to provide a description of baseline characteristics and outcomes of PLHIV (re)initiating ART in primary and secondary health facilities in Blantyre district, Malawi and Lesotho and to allow for an informal comparison between PLHIV (re)initiating ART with and without presumptive TB according to the W4SS. A further objective is to explore and describe the diagnostics, treatment and outcome of PLHIV with presumptive TB not eligible for participation in the SaDAPT RCT (i.e. due to reported pregnancy, signs of CNS disease or positive CrAg test) in routine care in primary and secondary health facilities in Blantyre district, Malawi and Lesotho. The ART initiation cohort will provide insights into the current management and outcomes of PLHIV (re)initiating ART in Malawi and Lesotho beyond the narrow question about timing of ART initiation in presumptive TB addressed with the SaDAPT RCT. The ART initiation cohort's objectives are thus not directly linked to the SaDAPT RCT's objectives, but add to them.

### 15.3 Study design and duration

The ART initiation cohort is an observational, prospective cohort study. Enrolment period for the ART initiation cohort is identical to the one for SaDAPT RCT, thus starting in October 2022 and ending when sample size for the SaDAPT RCT has been reached approximately 18 months later. Follow-up for the ART initiation cohort is maximum 24 months.

### 15.4 Study population and rationale

#### 15.4.1 Inclusion and exclusion criteria

PLHIV (re)initiating ART at one of the study facilities during the recruitment period of the SaDAPT RCT meeting the following criteria will be included in the ART initiation cohort:

##### Inclusion criteria

- 12 years or older
- HIV-positive
- Not taking ART (naïve or reported no ART intake since 90 days or more)
- Planning to continue care at the study facility for at least 30 weeks
- Willing and able to consent (age 18 years or older) or assent with guardian consent (age 12-17 years)

## Exclusion criteria

- Medical condition requiring referral to a higher level health facility at enrolment

The ART initiation cohort consists of consenting ART (re)initiators at the study sites, independent of whether they have presumptive TB or whether other exclusion criteria of the SaDAPT trial are present. Participants of the SaDAPT trial are part of the ART initiation cohort. The SaDAPT RCT ends after a follow-up period of maximum 40 weeks with the assessment of the trial's primary endpoint. After the termination of the follow-up of the randomized-controlled intervention, the participants of the SaDAPT RCT, will remain in care at the study facility and will be followed-up observationally like the other participants of the ART initiation cohort that were not part of the SaDAPT RCT.

### 15.4.2 Estimated sample size

No sample size calculations are performed. The enrolment will last until sample size for the SaDAPT RCT has been reached. We estimate the prevalence of any TB symptom among PLHIV (re)initiating ART between 30%-45%, thus sample size is estimated to reach between 1300 and 1800 participants.

## 15.5 Study procedures

Enrolment and follow-up of the ART initiation cohort will be performed by the study staff that is responsible for implementation of the SaDAPT trial, using the same data collection tool.

### 15.5.1 Screening and informed consent

The screening and informed consent process for the ART initiation cohort will follow the same principles as the processes for the SaDAPT trial and will be conducted by the same site investigators: Potential participants will be approached by a site investigator and asked to give verbal consent to study screening (equivalent to SaDAPT trial screening). As a result of the study screening, individuals will be classified either as not being eligible for any study, as being eligible for the ART initiation cohort only, but not for the SaDAPT trial or as being eligible for the SaDAPT trial (and therefore also for the ART initiation cohort).

Individuals meeting the criteria for participation in the SaDAPT trial, will be approached for informed consent for participation in the SaDAPT trial. The SaDAPT trial consent includes consent to further observational follow-up within the ART initiation cohort after termination of the SaDAPT follow-up period.

Individuals meeting the criteria for participation in the ART initiation cohort, but who do not meet the criteria for participation in the SaDAPT trial (for example due to absence of TB symptoms or due to a positive CrAg test) or who refuse participation in the SaDAPT trial, are being approached for consent to participate in the ART initiation cohort. As for the SaDAPT trial, the site investigator will discuss the cohort study with individuals identified as potential participants (and their guardian if age 12-17 years). An ART initiation cohort-specific information leaflet will be provided and all possible questions will be answered before the specific ICF may be signed. Consideration will be given to ensuring privacy and confidentiality. See section 11.3 for information about informed consent process, including for vulnerable participants as the same procedures apply for the ART initiation cohort

### 15.5.2 Baseline assessment

Enrolment will take place in an environment as private as possible, within the constraints of the clinic setting, so that confidentiality can be assured.

On enrolment, the following procedures will be performed:

- Brief clinical history and physical examination including:
  - o HIV, ART and TB clinical history
  - o Sociodemographic characteristics, health status, comorbidities and co-medications
  - o Measurement of height and weight with determination of BMI and vital signs
  - o Pregnancy status
  - o Screening for signs of CNS disease

- Collection of DBS in Malawi and collection of plasma sample in Lesotho (DBS only if venous blood draw is not possible)

### 15.5.3 ART initiation

Routine staff will decide on timing of ART initiation depending on clinical situation and following national guidelines. Study staff will document the date of ART initiation and relevant circumstances.

### 15.5.4 Follow-up

HIV care will be provided by routine clinic staff, according to national guidelines with no intervening of study staff.

Study staff will document date of ART initiation, dates and results of possible TB investigations, dates of ART refills, dates and results of VLs and information about possible relevant complications based on data recorded by routine staff in the respective clinical registries. As for the SaDAPT trial, there will be register reviews 28 days and 30 weeks after enrolment to ensure complete and correct data collection. At the time of the 6-months routine VL measurement (window 22-30 weeks after enrolment), the same clinical assessment will be performed as for the SaDAPT trial participants and plasma samples (or DBS if blood draw not possible) will be collected at the study sites in Lesotho. At the study sites in Malawi in participants without a documented VL between 22 and 30 weeks after enrolment, a DBS might be collected (collection of plasma samples is not possible due to resource constraints). A subsample of ART initiation cohort participants without documented VL results will be traced back via phone calls and home visits to ascertain their outcome.

One year (56 weeks) and two years (112 weeks) after enrolment, register reviews will be conducted to assess the number of participants retained in care, the rate of viral suppression and the occurrence of SAEs and AESIs up to the respective time points. Again, a subsample of participants without documented VL result one and two years after enrolment will be traced back, if resources allow. In Lesotho plasma samples may be collected one and two years after enrolment if resources allow.

## 15.6 Safety considerations

The ART initiation cohort does not entail any intervention; all routine ART and TB services will remain as usual. Thus, no AE is likely to be related to study participation.

AEs will be solicited and recorded in the same way as for members of the SaDAPT trial. As all AEs are likely to be unrelated to study participation they do not need to be reported. Deaths should be reported as for the SaDAPT trial (section 7.1.6).

No monitoring, no DSMB and no formal interim analysis are planned for the ART initiation cohort.

## 15.7 Data management

For data management, data safety and confidentiality, the same procedures apply as for the SaDAPT trial (see section 8).

## 15.8 Statistics

Cohort baseline characteristics and outcomes will be presented descriptively, no formal statistical analysis will be performed.

## 15.9 Ethical considerations

### 15.9.1 Risk benefit assessment and compensation

The ART initiation cohort is purely observational. Risk from participation is minimal. Data confidentiality will be maintained. Participants may benefit from improved care through signposting of missing HIV and/or TB drug prescription for eligible participants to routine staff and through re-linkage to care during

the tracing of participants lost to follow-up. The evidence generated with this cohort study will contribute valuable evidence to the understanding of current management and outcomes of PLHIV (re)initiating ART in southern Africa. Participants in Malawi will receive a compensation of 1000 Malawi kwacha (circa 1.25 US dollar), no compensation will be paid to participants in Lesotho.

#### **15.9.2 Rationale for inclusion of vulnerable subjects**

We will include adolescents aged 12 to 17 years if assent and guardian consent is provided and consenting pregnant women in the ART initiation cohort. Both groups are often excluded from interventional studies due to safety or ethical concerns. Evidence on these subgroups to improve treatment approaches is required as for all other PLHIV. We will include them in this observational study, to generate some evidence on current management and outcomes of these specific subgroups of PLHIV without exposing them to the risk of an intervention.

## 16 SERUM PROTEOME SUB-STUDY: PREDICTION OF CLINICAL PHENOTYPES IN PEOPLE LIVING WITH HIV USING THE SERUM PROTEOME

This is a laboratory-based sub-study that will be conducted using the plasma samples and clinical data collected as part of SaDAPT trial and ART initiation cohort at the study sites in Lesotho.

### 16.1 Background and rationale

Mycobacterium tuberculosis (MTB) infection is ancient: models suggest that MTB might have emerged as a human pathogen around 400,000 years ago. Over this long period, MTB and humans have co-evolved to reach a balance; MTB infects many people—approximately 28% of the human population have been exposed to MTB—but over 90% of infected individuals do not develop disease. HIV infection remains one of the most important risk factors for developing active TB.

Diagnosis of active TB remains a challenge: PLHIV typically present with disseminated disease delaying appropriate treatment. An additional complication of HIV/TB co-infection is increased risk for IRIS after initiation of antiretroviral treatment. IRIS develops once HIV viremia is suppressed due to the reconstitution of the immune system. The recovering immune system over-reacts to ongoing infections (paradoxical IRIS) or recognizes infections which were previously not detected due the HIV induced immune suppression (unmasking IRIS). Predicting IRIS in PLHIV is impossible with current diagnostic methods.

In this sub-study, we will screen samples from the SaDAPT trial and the SaDAPT ART initiation cohort in Lesotho to map the landscape of circulating inflammatory markers using cutting edge proteomics in PLHIV with high risk of active TB and IRIS. The proteome will be deconvoluted using computational biology with the aim to develop diagnostics for active TB disease and predictors for IRIS.

A test based on circulating proteins to predict IRIS has significant advantages: proteins are easy to measure in peripheral blood which allows the development of a point of care test in a straightforward way. In turn, a point of care test to predict IRIS would facilitate prevention and treatment of IRIS.

Today, IRIS recommendations are primarily based on disease entities. For example, in the case of TB meningitis and TB pericarditis, steroid treatment as prevention for IRIS is recommended. However, it is well known that lymph node TB is also prone to IRIS type reactions. However, for lymph node TB steroids are generally not recommended. A point of care test to predict IRIS would allow personalizing the clinical approach to IRIS prevention by going beyond arbitrary disease entities.

This sub-study has the potential to directly affect clinical care of a highly vulnerable population at high risk for unfavorable outcomes.

### 16.2 Objectives

- To diagnose active TB in PLHIV presenting with clinical symptoms
- To predict IRIS in PLHIV undergoing antiretroviral treatment
- To explore factors associated with control or progress of both TB and HIV infections

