### 2.2 Same-day ART initiation

An important element to improve access to ART is the implementation of rapid, if possible same-day initiation (SDI) of ART in persons found HIV positive. Rapid or same-day ART initiation improves retention in care, viral suppression and survival compared to a delayed start of ART for people with advanced HIV disease. In addition to improving individual health outcomes, SDI also reduces the risk of sexual transmission of HIV. The World Health Organization (WHO) as well as guidelines in the US, Europe and southern Africa including Lesotho and Malawi thus recommend rapid, possibly same-day, ART initiation for patients without contraindications, who are ready and willing to start ART immediately.

Individuals with advanced HIV disease or opportunistic infections may benefit particularly from rapid ART initiation and the subsequent suppression of HIV replication and reconstitution of CD4 cell mediated immunity. At the same time, patients with advanced HIV disease or opportunistic infections, especially TB, are at increased risk of developing immune reconstitution inflammatory syndrome (IRIS) after initiation of ART. IRIS is an acute inflammatory condition often presenting with worsening or new onset of symptoms of underlying opportunistic infections, caused by an exaggerated inflammatory response after restoration of immunity through ART. The risk for development of IRIS increases with lower levels of CD4 cells at baseline, the presence of opportunistic infections, especially TB, and with earlier initiation of ART. IRIS is most deleterious in cases of central nervous system (CNS) involvement in the form of TB or cryptococcal meningitis. Therefore, rapid initiation of ART does not improve overall mortality in patients with CNS infections, but increases incidence of severe adverse events. For manifestations of opportunistic infections such as TB outside the CNS, IRIS is less severe often resolving without medical care and optimal timing for initiation of ART remains unclear.

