### 2.3 ART initiation in PLHIV with presumptive TB

WHO recommends a four-symptom screening approach including cough, fever, night sweat and weight loss for clinical routine TB-screening among PLHIV. PLHIV presenting with at least one of the four symptoms are defined as having presumptive TB, and should subsequently undergo microbiological TB investigations to refute or confirm the diagnosis of active TB. Routine TB investigations typically consist of providing the patient two or three sputum bottles with the instruction to return with filled bottles the next day. If the patient returns with the sputum bottles, the samples are sent for analysis using nucleic acid amplification tests (Xpert MTB/RIF (Ultra)). The prevalence of presumptive TB among PLHIV not

taking ART has been estimated at 71% in a systematic review with considerable variation between studies. Studies in Kenya and South Africa have shown that the subsequent bacteriological work-up confirmed the presence of active TB in only 5%-19% of presumptive TB cases.

Until the release of a guideline update in 2021, WHO had recommended to delay initiation of ART in case of presumptive TB until TB has been investigated and TB treatment initiated if found TB-positive in order to reduce the risk of IRIS. This recommendation to defer ART for everyone with presumptive TB impairs access to same-day ART initiation for a large share of PLHIV. Whereas from a medical perspective delaying ART by a few days until a TB workup has been completed is reasonable, it may cause harm in resource-limited settings where delays between HIV diagnosis and ART initiation are associated with attrition from care, pre-treatment mortality and substantial out-of-pocket costs for patients, especially in remote areas where walking distances or transport costs to clinics are high. In these settings, offering same-day ART to PLHIV with presumptive TB while TB work-up is done in parallel may be a valuable strategy to engage and retain more patients in care and thus improve overall clinical outcomes.

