#### Paradoxical TB IRIS

##### (A) Antecedent requirements

Both of the two following requirements must be met:

- Diagnosis of tuberculosis: the tuberculosis diagnosis was made before starting ART and this should fulfil WHO criteria for diagnosis of smear-positive pulmonary tuberculosis, smear-negative pulmonary tuberculosis, or extra-pulmonary tuberculosis
- Initial response to tuberculosis treatment: the patient's condition should have stabilised or improved on appropriate tuberculosis treatment before ART initiation—e.g., cessation of night sweats, fevers, cough, and weight loss. (Note: this does not apply to patients starting ART within 2 weeks of starting tuberculosis treatment since insufficient time may have elapsed for a clinical response to be reported)

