#### Unmasking tuberculosis-associated IRIS

Patient is not receiving treatment for tuberculosis when ART is initiated and then presents with active tuberculosis within 3 months of starting ART

AND one of the following criteria must be met:

- Heightened intensity of clinical manifestations, particularly if there is evidence of a marked inflammatory component to the presentation. Examples include tuberculosis lymphadenitis or tuberculosis abscesses with prominent acute inflammatory features, presentation with pulmonary tuberculosis that is complicated by respiratory failure due to adult respiratory distress syndrome, and those who present with a marked systemic inflammatory syndrome related to tuberculosis.
- Once established on tuberculosis treatment, a clinical course that is complicated by a paradoxical reaction

The study team will gather as much information as possible about all possible AESIs. Information will be gathered about TB diagnoses, timing of ART initiation (relative to TB diagnosis and treatment), clinical course (including documentation of relevant diagnostic and therapeutic activities by routine clinical staff), and alternative explanations for clinical symptoms. This information (including judgement of study physician, National PI or delegate) will be presented to an independent expert clinical committee for adjudication about likelihood that symptoms are consistent with TB-IRIS. The adjudication committee will be blinded to arm allocation.

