### 16.3 Approach

#### 16.3.1 Sample collection and assessment of the clinical phenotype

For this sub-study, plasma samples from the SaDAPT trial and the ART initiation cohort collected at study sites in Lesotho will be used. For the assessment of the clinical phenotype (i.e. CD4 cell count, VL, occurrence of active TB or IRIS), the data collected during the SaDAPT trial and the ART initiation cohort as described above will be used. No clinical data or samples other than outlined in the protocol sections of the SaDAPT trial and the ART initiation cohort will be collected for this sub-study.

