### 16.3.3 Deconvolution of proteomic maps using computational biology

This study requires deconvolution of high dimensional data (the proteome) into a clinically meaningful predictor. We will use advanced statistical methods to deconvolute the high dimensional data. Specifically, we will primarily focus on the development of a proteome based voting score, given our publishing record and our experience with the diagnostic score development based on the published pairwise support vector machine (SVM) parameters and the robustness of the approach. However, we will also employ random forest models and deep neuronal network approaches and compare the diagnostic accuracy of different techniques.

We will follow a training – test cohort strategy whereby approximately 2/3 of all samples will be used as input into the machine learning algorithms. The remaining 1/3 of samples will be used as test set to evaluate the performance of the training set. Sample allocation to test and training sets is randomized. For external validation, we will test our proteome signature against already published proteome signatures in patients with active TB and HIV infection.

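### As section 16 is written, accuracy for predicting IRIS is confounded with TB detection: the only IRIS recorded is TB-IRIS, and no evaluation among people with TB is described

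*Protocol*

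**What the plan says.** Protocol 16.2 lists two prediction objectives with different populations. The TB objective is "To diagnose active TB in PLHIV presenting with clinical symptoms". The IRIS objective is wider: "To predict IRIS in PLHIV undergoing antiretroviral treatment".

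On material, 16.3.1 says that "plasma samples from the SaDAPT trial and the ART initiation cohort collected at study sites in Lesotho will be used". It takes the clinical phenotype, IRIS included, from data already collected in the trial and cohort, and adds no clinical data. The cohort enrols people with or without presumptive TB (15.4.1) and records adverse events in the same way as the trial (15.6).

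On method, 16.3.3 gives a single random split of all samples, roughly two thirds to train and one third to test, and says the team will "compare the diagnostic accuracy of different techniques". External validation is against published signatures from patients with active TB and HIV.

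On the outcome, the only IRIS event defined is the adverse event of special interest, which is TB-IRIS (7.1.1). The paradoxical form requires "Diagnosis of tuberculosis: the tuberculosis diagnosis was made before starting ART". In the unmasking form the patient is not on TB treatment at ART start and "then presents with active tuberculosis within 3 months of starting ART" (7.1.3).

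**The concern.** Every recorded IRIS case has TB, while most people in the sample set probably do not. In such a set, comparing IRIS with no IRIS is largely a comparison of TB with no TB. A score built for the first objective would therefore perform well on the second without any information on who among people with TB develops IRIS.

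Nothing in section 16 would reveal this. It describes no evaluation within TB, no stratification by TB and no benchmark. The external check uses active-TB signatures, which a TB detector would pass. Yet Protocol 2.2 already names simple predictors: "The risk for development of IRIS increases with lower levels of CD4 cells at baseline, the presence of opportunistic infections, especially TB", and also earlier ART.

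The use proposed in 16.1 is to individualise IRIS prevention instead of relying on disease categories, and its examples are different forms of TB. That use needs a score that separates TB with IRIS from TB without IRIS. Accuracy in all samples cannot show this.

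**Working it through.** Section 16 states no sample size, IRIS rate or accuracy target, so it has no figure to reproduce. The check asks how a score that depends on TB status alone would perform for IRIS in the sample set described.

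**Inputs**
- *p*, the TB share of the samples. Protocol 2.3 reports that bacteriological work-up "confirmed the presence of active TB in only 5%-19% of presumptive TB cases". The share in the Lesotho samples is not given. Clinical and x-ray diagnoses would raise it, and cohort members without symptoms may lower it.
- *r*, the IRIS risk among people with TB. The documents do not give it. Assumed 10%, with a range of 5% to 30%.

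**Formulas**
- Share of people without IRIS who have TB: w = p(1 − r)/(1 − pr).
- Perfect TB detector with no IRIS information: sensitivity for IRIS 1, specificity 1 − w, AUC 1 − w/2, positive predictive value r.
- TB-only score with AUC *A* for TB: AUC for IRIS = 0.5w + A(1 − w). A binary test with sensitivity and specificity of 80% has A = 0.80.
- Among people with TB, every such score has an AUC of 0.50 for IRIS.

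**Results at r = 10%**

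| p | w | Perfect TB detector | 80%/80% TB test |
|---|---|---|---|
| 5% | 0.05 × 0.90/0.995 = 0.0452 | 0.977 | 0.786 |
| 12% | 0.12 × 0.90/0.988 = 0.1093 | 0.945 | 0.767 |
| 19% | 0.19 × 0.90/0.981 = 0.1743 | 0.913 | 0.748 |

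**Sensitivity to the assumptions**
- For r from 5% to 30%, the perfect detector has an AUC of 0.976 to 0.982 at p = 5% and 0.909 to 0.929 at p = 19%. The unknown *r* matters little.
- At p = 30% (assumed), it falls to 0.855 to 0.885.
- With p from 5% to 19% and r from 5% to 30%, a TB AUC of 0.90 gives an IRIS AUC of 0.83 to 0.89, and a TB AUC of 0.75 gives 0.70 to 0.74.
- Simulations of 1,000,000 people per scenario agree. With TB AUC 0.90, p = 19% and r = 30%, the IRIS AUC was 0.843 in all samples (formula 0.844) and 0.499 within TB.

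**Events available**

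The cohort estimate in 15.4.2 is 1300 to 1800 over both countries. The Lesotho share is not stated, so take 650 (half of 1300, assumed) to 1800 (all).
- Low end, p = 5% and r = 5%: 650 × 0.05 = 32.5 with TB, × 0.05 = 1.6 IRIS cases, about 0.5 of them in the test third.
- High end, p = 19% and r = 30%: 1800 × 0.19 = 342 with TB, × 0.30 = 102.6 IRIS cases, about 34 of them in the test third.

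**The case against.** The strongest reply is that section 16 is an outline. The split in 16.3.3 serves every objective and names no analysis set or accuracy measure for IRIS. It cannot apply literally to each objective: the TB objective is limited to people with symptoms, and stored plasma includes week-26 samples (6.9, 15.5.4), which would normally fall after the three-month TB-IRIS window. SAP 6.4 says that sub-study analyses are described elsewhere. This stands in part. A reader might infer that the protocol commits to scoring IRIS in every participant. It does not: the set is inferred from the objective and the split, and covers Lesotho only. But the deferral repairs nothing in the text available.

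Second, people starting ART without a TB diagnosis are a legitimate population for predicting unmasking IRIS. That is right. Restricting that form to people who later show active TB would condition on a future event, so one within-TB analysis cannot serve both forms.

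Third, within-TB estimates may rest on very few events. That is true, but an all-sample analysis rests on the same cases and only makes the scarcity harder to see.

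Fourth, reporting the positive predictive value would expose the problem, since for a perfect TB detector it equals only *r*. Section 16.3.3 does not promise it.

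**Conclusion.** The point holds as confounding by TB status, in a plan that describes nothing to separate the two. A TB-only score with an AUC of 0.50 within TB would show about 0.91 to 0.98 in all samples if TB detection is perfect, and about 0.75 to 0.79 at 80% sensitivity and specificity. This rests on a TB share of 5% to 19%, an assumed IRIS risk of 10% in TB, and evaluation on the undivided Lesotho set.

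A reader might go further and infer that the sub-study will report an excellent IRIS predictor. The documents do not support that. Excellent values need a near-perfect TB score, and they fall if clinical diagnoses raise the TB share or if unmasking TB is undetectable at baseline. Nor can one conclude that a within-TB AUC must be the headline result, because the event count may be too small.

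The consequence is limited to what the sub-study can claim. The trial's endpoints and randomised comparison are untouched. It is a worthwhile, inexpensive correction to make before the proteome analysis.

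**What to change.** In 16.2 and 16.3.3, or in the separate sub-study plan:

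- Call the outcome TB-IRIS.
- Use only samples taken before the event.
- For paradoxical TB-IRIS, report accuracy among participants with TB diagnosed before ART start.
- For unmasking TB-IRIS, report accuracy among participants who start ART without TB treatment. Show separately how far the score distinguishes TB with IRIS from TB without IRIS.
- Set any all-sample figure beside a benchmark of TB status and ART timing, and report the gain over it. Add CD4 count where available: it is listed at baseline for trial participants (6.3) but not in the cohort's baseline list (15.5.2).
- State the number of TB-IRIS cases behind each estimate.

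This needs no new samples or data. The cost is that within-TB estimates rest on few events, may be too imprecise to serve as a headline, and will look less favourable.
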